5.7 Criteria for Patient Discontinuation

Patients may be discontinued from study treatment and assessments at any time. Specific reasons for discontinuing a patient for this study are:

- Voluntary discontinuation by the patient who is at any time free to discontinue his/her participation in the study, without prejudice to further treatment.
- Safety reason as judged by the Principal Investigator
- Major protocol deviation
- Incorrect enrolment ie, the patient does not meet the required inclusion/exclusion criteria for the study

- Patient lost to follow-up
- Patient's non-compliance to study treatment and/or procedures

5.8 Procedures for Discontinuation

5.8.1 Patient Discontinuation

Patients who withdraw or are withdrawn from the study, will stop further treatment according to protocol.

Patients who are withdrawn from study treatment will be followed up at local hospitals according to standard procedure.

If possible, a final assessment shall be made (end of study visit). The reason for discontinuation shall be recorded. The patients will have follow-up for any significant adverse events until the outcome either is recovered or resolved, recovering/resolving, not recovered/not resolved, recovered/resolved with sequelae, fatal or unknown.

All patients randomized will be included in the study population.

Patients who withdraw or are withdrawn from the study after randomisation cannot be replaced.

5.8.2 Trial Discontinuation

The whole trial may be discontinued at the discretion of the PI or the sponsor in the event of any of the following:

- Occurrence of AEs unknown to date in respect of their nature, severity and duration
- Medical or ethical reasons affecting the continued performance of the trial
- Difficulties in the recruitment of patients

The sponsor and principal investigator(s) will inform all investigators, the relevant Competent Authorities and Ethics Committees of the termination of the trial along with the reasons for such action. If the study is terminated early on grounds of safety, the Competent Authorities and Ethics Committees will be informed within 15 days.

5.9 Laboratory Tests

Blood samples will be taken to determine CRP, Hb, HCT, WBC (incl.differential counting), PLT, Na, K, Ca, creatinine, ASAT, ALAT, LD, ALP, γ GT, INR, albumin, bilirubin CEA and CA 19-9. The samples will be collection and handed in accordance with hospital/laboratory standard procedures.

5.10 Assessment of Efficacy

Overall survival, liver resection rates and surgical complications will be recorded from patient medical records.

Assessment of tumor response (prior to resection or transplant): tumor response will be assessed according to RECIST version 1.1, based on CT scans of thorax, abdomen and pelvis. This procedure cannot be blinded as the HAI catheter will show on all CT series.

Chemotherapy related toxicity will be evaluated using NCI-CTC v. 5.0, grade 3-5 related to systemic chemotherapy will be assessed.

Surgical complication will be assessed by Accordion grading system, only grade 3-6 will be recorded.

Quality of life will be assessed by EORTC QLQC30 and EQ5D.

Biomedical marker related to clinical outcome will be developed based on blood samples and liver biopsies collected

5.11 Safety and Tolerability Assessments

Safety will be monitored by the assessments described below as well as the collection of AEs at every visit. Significant findings that are present prior to the signing of informed consent must be included in the relevant medical history/ current medical condition page of the CRF. For details on AE collection and reporting, refer to Section 6.

For the assessment schedule refer to Flow chart in Section 5.6.

5.12 End of study (EOS)

Last Patient Last Visit is defined as End of Study.

6 SAFETY MONITORING AND REPORTING

The investigators are responsible for the detection and documentation of events meeting the criteria and definition of an adverse event (AE) or serious adverse event (SAE). Each patient will be instructed to contact the investigators immediately should they manifest any signs or symptoms they perceive as serious.

The methods for collection of safety data are described below.

6.1 Definitions

6.1.1 Woman of childbearing potential (WOCBP)

A woman is considered of childbearing potential (WOCBP), i.e. fertile, following menarche and until becoming post-menopausal unless permanently sterile. Permanent sterilisation methods include hysterectomy, bilateral salpingectomy and bilateral oophorectomy.

A postmenopausal state is defined as no menses for 12 months without an alternative medical cause. A high follicle stimulating hormone (FSH) level in the postmenopausal range may be used to confirm a post-menopausal state in women not using hormonal contraception or hormonal replacement therapy. However in the absence of 12 months of amenorrhea, a single FSH measurement is insufficient.

6.1.2 Birth Control Methods

One of the highly effective methods of contraception listed below is required during study duration and until the end of relevant systemic exposure, defined as one month after the end of study treatment.

Combined (estrogen and progestogen containing) hormonal contraception associated with inhibition of ovulation 1:

- oral

- intravaginal
- transdermal

Progestogen-only hormonal contraception associated with inhibition of ovulation 1:

- oral
- injectable
- implantable 2

Intrauterine device (IUD)

Intrauterine hormone-releasing system (IUS)

Bilateral tubal occlusion

A vasectomized partner is a highly effective contraception method provided that the partner is the sole male sexual partner of the WOCBP and the absence of sperm has been confirmed. If not, an additional highly effective method of contraception should be used.

Sexual abstinence is considered a highly effective method only if defined as refraining from heterosexual intercourse during the entire period of risk associated with the study drug. The reliability of sexual abstinence needs to be evaluated in relation to the duration of the study and the preferred and usual lifestyle of the participant.

6.1.3 Adverse Event (AE)

An AE is any untoward medical occurrence in a patient administered a pharmaceutical product and which does not necessarily have a causal relationship with this treatment.

An adverse event (AE) can therefore be any unfavorable and unintended sign (including an abnormal laboratory finding), symptom, or disease temporally associated with the use of a medicinal (investigational) product, whether or not related to the medicinal (investigational) product.

The term AE is used to include both serious and non-serious AEs.

If an abnormal laboratory value/vital sign are associated with clinical signs and symptoms, the sign/symptom should be reported as an AE and the associated laboratory result/vital sign should be considered additional information that must be collected on the relevant CRF.

6.1.4 Serious Adverse Event (SAE)

Any untoward medical occurrence that at any dose:

- Results in death
- Is immediately life-threatening
- Requires in-patient hospitalization or prolongation of existing hospitalization
- Results in persistent or significant disability or incapacity
- Is a congenital abnormality or birth defect
- Is an important medical event that may jeopardize the subject or may require medical intervention to prevent one of the outcomes listed above.

A pre-planned hospitalization admission (ie, elective or scheduled surgery arranged prior to the start of treatment) for pre-existing condition is not considered to be a serious adverse event.

6.1.5 Suspected Unexpected Serious Adverse Reaction (SUSAR)

Suspected Unexpected Serious Adverse Reaction (SUSAR) is defined as any serious adverse reaction where the nature or severity is not consistent with the product information mentioned in the Reference Safety Information in the SPC and for HAI in the publication by Pak and colleagues

6.1.6 Serious Adverse Reaction

A Serious adverse reaction (SAR) is any untoward and unintended response in a subject to an investigational medicinal product which is related to any dose administered to that subject, and meets the criterias for SAE above.

6.2 Recording procedure

6.2.1 Adverse Events

All adverse events related to standard systemic chemotherapy and all adverse events related to FUDR pump administration will be recorded in the Case Report Form (CRF).

6.2.2 Disease Progression/Recurrence

Death due to progressive disease is to be recorded as an SAE.

Only (unexpected) SARs related to IMPs need to be reported to the Competent Authorities, by using a CIOMS reporting form.

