5.6.3 Progressive disease or toxicity

In the case of progressive disease (PD) in the systemic chemotherapy arm, this treatment will be halted and shifted to 3rd chemotherapy as appropriate or to best supportive care (BSC). In the case of PD in the HAI-group, systemic chemotherapy will be changed to 3rd line as appropriate and the use of pump is discontinued. In the case of PD in the transplant group, listing is upheld but chemotherapy is changed to 3rd line as appropriate until available organ is available. In the case of toxicity a change in systemic chemotherapy to 3rd line is attempted and if unaltered toxicity, halted.

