6.2.3 Duration Period for Reporting AE and SAE

Any new primary cancer (non-related to the cancer under study) should be recorded in the CRF.

For each patient the standard time period for collecting and recording of AE and SAEs in the CRF (reporting of SAE to sponsor) will begin at start of study treatment and will continue for at least 30 days following the last dose of study treatment for each patient in patients receiving FUDR.

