6.2.4 Recording of Adverse Events

All adverse event(s) independent of treatment arms will be recorded by study personell in the CRF as required below:

- The nature of the event(s) will be described by the investigator in precise standard medical terminology (i.e. not necessarily the exact words used by the patient).
- The duration of the event will be described in terms of event onset date and event ended data.
- The intensity of the adverse event: NCI-CTC 5.0
- The Causal relationship of the event to the study medication will be assessed as one of the following

Unrelated:

There is not a temporal relationship to investigational product administration (too early, or late, or investigational product not taken), or there is a reasonable causal relationship between non-investigational product, concurrent disease, or circumstance and the AE.

Unlikely:

There is a temporal relationship to investigational product administration, but there is not a reasonable causal relationship between the investigational product and the AE.

Possible:

There is reasonable causal relationship between the investigational product and the AE. Dechallenge information is lacking or unclear.

Probable:

There is a reasonable causal relationship between the investigational product and the AE. The event responds to dechallenge. Rechallenge is not required.

Definite:

There is a reasonable causal relationship between the investigational product and the AE.

- Action taken
- The outcome of the adverse event – whether the event is resolved or still ongoing.

It is important to distinguish between serious and severe AEs. Severity is a measure of intensity whereas seriousness is defined by the criteria in Section 8.1. An AE of severe intensity need not necessarily be considered serious. For example, nausea that persists for several hours may be considered severe nausea, but is not an SAE. On the other hand, a stroke that results in only a limited degree of disability may be considered a mild stroke, but would be an SAE.

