6.4 Procedures in Case of Emergency

Administration of study treatment will be performed in a setting with emergency medical facilities and staff who are trained to monitor for and respond to medical emergencies. Medical emergencies during the study will be handled according to standard operating procedure at Department of Transplantation Medicine/ Department of HBP surgery at Rikshospitalet

All adverse events and serious adverse events will be recorded during the trial until resolved.

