8.5.3 Safety analyses

The adverse events will be presented descriptively by means of frequency and percentages to evaluate both the rate of incidence and event occurrence among the different treatment groups. The descriptive tables will be presented with respect to intensity, seriousness and relationship to the treatment.

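### Deaths from progression count as SAEs and are not separated in the by-arm safety tables, so the all-cause serious and fatal rows will largely repeat the primary endpoint; an end of AE/SAE collection is stated only for patients receiving FUDR.

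*Protocol*

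**What the plan says.** - **Progression deaths.** Protocol 6.2.2: "Death due to progressive disease is to be recorded as an SAE". The sentence carries no limit of arm or time. It agrees with 6.1.4, under which any event resulting in death is serious.
- **Safety tables.** Protocol 8.5.3 describes adverse events by treatment group with frequencies and percentages: "The descriptive tables will be presented with respect to intensity, seriousness and relationship to the treatment". It does not say how deaths from the disease under study are shown.
- **Collection window.** Protocol 6.2.3 says collection "will begin at start of study treatment and will continue for at least 30 days following the last dose of study treatment", and then qualifies this with "for each patient in patients receiving FUDR". No end is stated for anyone else.
- **Recording in all arms.** Protocol 6.2.4: "All adverse event(s) independent of treatment arms will be recorded by study personell in the CRF". Protocol 6.4 adds: "All adverse events and serious adverse events will be recorded during the trial until resolved".
- **Toxicity endpoint.** Table 1 lists grade III-V toxicity. Section 5.10 limits the assessed grade 3-5 events to those related to systemic chemotherapy.
- **Primary endpoint.** Overall survival at two years after randomization (sections 2 and 8.5.1), with death from any cause as the event.

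**The concern.** In this population most deaths will be from the cancer, and the plan expects very different death rates between arms. If those deaths sit unmarked among the serious and fatal events, the by-arm safety table mainly shows efficacy a second time. An arm with better survival then looks safer even if its treatment causes as much harm or more. What matters here is whether the pump and floxuridine add serious harm. With about 18 patients per arm, a few serious biliary or pump events in the HAI arm could be outweighed in the totals by cancer deaths in control. Section 6.3.1 also has the sponsor judge risk and benefit partly from SAE reports.

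The window adds a second problem. After progression in the HAI arm, "systemic chemotherapy will be changed to 3rd line as appropriate and the use of pump is discontinued". A cancer death months later may lie beyond the stated 30-day minimum for that patient, whereas no end at all is stated for a control patient with the same course.

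**Working it through.** **Inputs (section 8.1).** Two-year survival of 30% (standard care), 75% (HAI) and 90% (transplant); 18 + 18 + 9 = 45 randomised. The safety sections give no figures of their own.

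**The plan's own sample size.** With n per arm = (1.96 + 0.84)² × [p1(1−p1) + p2(1−p2)] / (p1−p2)²:
- 30% v 75%: 7.849 × (0.21 + 0.1875) / 0.2025 = 15.4, so 16
- 30% v 90%: 7.849 × (0.21 + 0.09) / 0.36 = 6.5, so 7
- 16 + 16 + 7 = 39; 39 × 1.15 = 44.85, so 45

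The stated numbers reproduce, so the arm sizes and rates below are those of the design.

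**Expected deaths by two years, n × (1 − survival).**
- Control: 18 × 0.70 = 12.6
- HAI: 18 × 0.25 = 4.5
- Transplant: 9 × 0.10 = 0.9
- Total 18.0, of which 12.6 / 18.0 = 70% in control

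**Progression deaths recorded as SAEs.** Assumption, not in the protocol: 80-100% of deaths are from progression. If all are recorded in every arm:
- Control: 12.6 × 0.8 to 12.6 × 1.0 = 10.1-12.6
- HAI: 4.5 × 0.8 to 4.5 × 1.0 = 3.6-4.5
- Transplant: 0.9 × 0.8 to 0.9 × 1.0 = 0.7-0.9

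This gap is the assumed survival benefit and nothing else. If HAI had no effect on survival (30% in both arms), the figures would be 10.1-12.6 in each.

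**Effect on patients with any SAE.** Suppose a share r of patients in each arm has a treatment-related SAE, independently of dying from progression (assumptions). The share with any SAE is 1 − (1 − r)(1 − d), where d is the share dying of progression.
- r = 0.2, 80% of deaths from progression: control 1 − 0.8 × 0.44 = 65%; HAI 1 − 0.8 × 0.80 = 36%
- r = 0.4, 100% from progression: control 1 − 0.6 × 0.30 = 82%; HAI 1 − 0.6 × 0.75 = 55%

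Harm from treatment is equal by construction, yet the serious rows differ by 27 to 29 percentage points.

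**Readings of the window.** Further assumption where a 30-day limit applies: 0-50% of progression deaths fall inside it.

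| Reading | Control | HAI |
|---|---|---|
| All recorded in both arms (6.2.2, 6.2.4, 6.4) | 10.1-12.6 | 3.6-4.5 |
| 30 days used as a cut-off for FUDR patients only | 10.1-12.6 | 0 to 4.5 × 0.5 = 2.25 |
| 30 days used as a cut-off in both arms | 0 to 12.6 × 0.5 = 6.3 | 0-2.25 |
| Control left out of the safety population, HAI fully recorded | 0 | 3.6-4.5 |

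The last row is possible because section 8.3 requires one dose of a study medication that is not defined, while section 5 defines the IMP as floxuridine and dexamethasone. The readings do not agree even on which arm carries more of these SAEs.

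**The case against.** **The relationship split already separates these deaths.** Section 8.5.3 also tabulates by relationship, and 6.2.4 treats an event explained by concurrent disease as unrelated. This stands in part. However, the causality scale in 6.2.4 is worded against the investigational product, and a product not taken leads to the unrelated category. Read literally, every control event is unrelated, chemotherapy toxicity included, even though 6.2.1 expects chemotherapy-related events to be recorded. The split therefore cannot reliably separate treatment harm from cancer death in control.

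**Grade 5 toxicity.** A reader might infer that the grade III-V toxicity endpoint is inflated too. The protocol does not support that: section 5.10 restricts it to events related to systemic chemotherapy, so a correctly attributed progression death stays out. Only the all-cause intensity table in 8.5.3 is affected.

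**Bias against control from the window.** A reader might infer that control cancer deaths are counted without end while HAI deaths are dropped, giving something like 13 of 18 against 0 of 18. That applies the rules unevenly. The 30 days is a minimum, 6.2.4 and 6.4 name no arm, and Table 7 gives the chemotherapy and HAI arms the same follow-up after progression. What stands is that the end of collection is unstated for patients not receiving FUDR.

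**Significance tests.** Fisher's exact test on 13/18 v 4/18 gives p = 0.007, but 8.5.3 is descriptive and plans no such test, and that contrast only restates the assumed survival benefit.

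**Recording deaths as SAEs is legitimate.** It follows 6.1.4, and section 6.5 makes a death in the HAI arm a matter for the DMC. Taking these deaths out of SAE recording altogether would rest on an open-label judgement of cause and might move a treatment-related death out of the safety data. This objection stands and shapes the fix.

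**Conclusion.** The point holds in a limited form. Progression deaths are SAEs without limit of arm or time, and the by-arm seriousness and intensity tables do not set them apart, so the all-cause serious and fatal rows will largely repeat the primary endpoint. The overlap is large but not complete, because the primary endpoint counts death from any cause. At the design rates, the size is about 10-13 such SAEs in control against 3.6-4.5 in HAI if all are recorded. That rests on the plan's survival figures and on an assumed 80-100% share of deaths from progression; with no survival benefit the imbalance disappears.

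Separately, the end of AE/SAE collection is stated only for patients receiving FUDR and does not fit with 6.2.4 and 6.4. Ascertainment may differ between arms, but the text does not settle by how much or in which direction. The consequence is for the descriptive safety comparison and the reading of risk and benefit. The primary analysis is untouched, and so is the chemotherapy-related toxicity measure, provided that deaths are correctly attributed.

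**What to change.** Reconcile sections 6.2.2, 6.2.3, 6.4 and 8.5.3:

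1. State one AE/SAE collection window, with its start and its end, for all arms.
2. Keep progression deaths in the SAE log, and flag them in the eCRF with cause of death.
3. Present the by-arm seriousness and intensity tables both with and without the flagged deaths.
4. Add a table of all-cause deaths by arm.
5. In the same revision, define study medication in 8.3 so that it is clear whether control patients belong to the safety population.

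The cost is protocol and SAP wording, one eCRF flag and a few extra tables. There is no effect on sample size or on the primary analysis. The downside is small: cause of death is judged open-label, but the unfiltered tables and the all-cause death table show the result without that judgement.

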6.2.3 Duration Period for Reporting AE and SAE

Any new primary cancer (non-related to the cancer under study) should be recorded in the CRF.

For each patient the standard time period for collecting and recording of AE and SAEs in the CRF (reporting of SAE to sponsor) will begin at start of study treatment and will continue for at least 30 days following the last dose of study treatment for each patient in patients receiving FUDR.

6.2.4 Recording of Adverse Events

All adverse event(s) independent of treatment arms will be recorded by study personell in the CRF as required below:

- The nature of the event(s) will be described by the investigator in precise standard medical terminology (i.e. not necessarily the exact words used by the patient).
- The duration of the event will be described in terms of event onset date and event ended data.
- The intensity of the adverse event: NCI-CTC 5.0
- The Causal relationship of the event to the study medication will be assessed as one of the following

Unrelated:

There is not a temporal relationship to investigational product administration (too early, or late, or investigational product not taken), or there is a reasonable causal relationship between non-investigational product, concurrent disease, or circumstance and the AE.

Unlikely:

There is a temporal relationship to investigational product administration, but there is not a reasonable causal relationship between the investigational product and the AE.

Possible:

There is reasonable causal relationship between the investigational product and the AE. Dechallenge information is lacking or unclear.

Probable:

There is a reasonable causal relationship between the investigational product and the AE. The event responds to dechallenge. Rechallenge is not required.

Definite:

There is a reasonable causal relationship between the investigational product and the AE.

- Action taken
- The outcome of the adverse event – whether the event is resolved or still ongoing.

It is important to distinguish between serious and severe AEs. Severity is a measure of intensity whereas seriousness is defined by the criteria in Section 8.1. An AE of severe intensity need not necessarily be considered serious. For example, nausea that persists for several hours may be considered severe nausea, but is not an SAE. On the other hand, a stroke that results in only a limited degree of disability may be considered a mild stroke, but would be an SAE.

